### **Routine study assessments.**

Patients will be seen at the study centre every 3 months for clinical evaluation and spirometry (post bronchodilator). For safety purposes patients will have urinalysis, FBC, U&E, LFT, glucose, amylase and a pregnancy test. Patients with TSC will have a their epilepsy reviewed. At 12 and 24 months patients will undergo full assessment as described under initial assessment.

### **Monthly phone contact.**

During months when no study visit is scheduled a telephone call will be made to participants to check compliance, reinforce safety advice and detect adverse events.

### **Combined safety endpoint.**

To avoid withholding treatment from those who decline rapidly in the placebo group, patients with either a fall from baseline FEV1 of 300 ml or a fall in resting SaO2 of 3% (on two occasions) will be unblinded and offered doxycycline according to the protocol. Those deteriorating in the doxycycline group will be withdrawn from the study at the discretion of the doctor. In addition, patients with either pneumothorax, increase in chylous effusion or bleeding angiomyolipoma will be withdrawn. Patients fulfilling these criteria for withdrawal, together termed the 'composite safety endpoint', will be compared between treatment arms.

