## Summary

We will perform a 2 year double blind, placebo controlled trial of doxycycline in 40 patients with LAM. The main endpoints will be change in FEV1, other measures of efficacy, safety and dose required to suppress MMP activity. After clinical evaluation, lung function, shuttle walk, QoL assessment, blood tests, serum and urine MMPs (termed full assessment) plus baseline chest X-ray patients will be randomised to doxycycline 50 mg od or placebo. Patients will be assessed at 2 weeks for a safety screen, every 3 months for clinical evaluation and spirometry and at 12 and 24 months for full assessment. At 1, 2 and 3 months urine zymography will be performed to see if MMPs are present in urine at the prescribed dose. Doxycycline will be increased to 50mg bd then 100 mg bd at monthly intervals up to three months after urine zymography has been performed. To avoid withholding treatment from those who decline rapidly, patients who, on two occasions, have either a fall from baseline FEV1 of 300 ml or fall in resting SaO2 of 3% will be assessed by an independent expert ([name]). Patients receiving placebo will be given the option of doxycycline according to protocol. Those receiving doxycycline the option of continuing in the study or withdrawal. These patients and those withdrawn due to recurrent pneumothorax, increase in chylous effusion or bleeding angiomyolipoma will be included in a composite safety endpoint and analysed on an intention to treat basis. Power calculations based on retrospective cohorts show that 20 patients per group will give 80% power to detect a 70 ml/year difference in FEV1 based an assumed SD for a fall in FEV1 of 75 ml/year. The mean slope of regression lines for FEV1 and FVC, plus change DLCO, shuttle walk distance and QoL in the doxycycline and placebo groups will be compared by parametric or non-parametric analysis dependent on data, time to composite safety endpoint by Kaplan-Meier analysis, complications and adverse events by Chi Square test.

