### Secondary endpoints

Comparison between the two groups for:

- Rate of change of FVC over 24 months
- Change in DLCO at 12 and 24 months
- Change in shuttle walk distance at 12 and 24 months
- Change in quality of life at 12 and 24 months
- Time to composite safety endpoint
- Number of complications - pneumothorax, pleural effusions, angiomyolipoma bleeding
- Number of respiratory infections
- Adverse effects

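### The protocol defines the composite safety endpoint in two inconsistent ways, and on one reading the same FEV1/SaO2 decline counts differently in the two arms

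*Protocol*

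**What the plan says.** Section 3, Combined safety endpoint, sets one trigger: a fall from baseline FEV1 "of 300 ml or a fall in resting" SaO2 of 3%, on two occasions. With the placebo group in view, it says that patients meeting it "will be unblinded and offered doxycycline according to the protocol". For the other arm it says: "Those deteriorating in the doxycycline group will be withdrawn from the study at the discretion of the doctor". Pneumothorax, an increase in chylous effusion or a bleeding angiomyolipoma leads to withdrawal in either arm. The section then closes: "Patients fulfilling these criteria for withdrawal, together termed the 'composite safety endpoint', will be compared between treatment arms".

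The Summary has the same trigger but routes patients through an independent expert. It continues: "Patients receiving placebo will be given the option of doxycycline according to protocol", and then "Those receiving doxycycline the option of continuing in the study or withdrawal". It forms the endpoint as follows: "These patients and those withdrawn due to recurrent pneumothorax, increase in chylous effusion or bleeding angiomyolipoma will be included in a composite safety endpoint", analysed by intention to treat.

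"Time to composite safety endpoint" is a listed secondary endpoint, analysed by Kaplan-Meier. In section 4, the FVC entry under Secondary endpoints speaks of patients who withdraw, including under the combined safety criteria, and analyses them up to withdrawal.

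**The concern.** A between-arm comparison needs an event that is recognised in the same way in both arms. The Combined safety endpoint section names the event through withdrawal, but after a decline withdrawal is discretionary on one arm and not described on the other. By the time the doctor exercises that discretion, the arm is known. The FVC entry in section 4 adds weight to this reading, because it too treats the combined safety criteria as a ground for withdrawal. The Summary points the other way.

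Two analysts could each follow the protocol and count different patients. On the withdrawal reading, a doxycycline patient who declines and is kept on would not be an event. A placebo patient with the same decline would be an event only if the offer of doxycycline is taken to count. An ineffective drug could then look protective or harmful, depending on the convention adopted.

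**Working it through.** **Step 1. The two definitions side by side, for an FEV1/SaO2 decline.**

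| | Summary | Combined safety endpoint |
|---|---|---|
| Trigger | 300 ml or 3%, on two occasions | the same |
| After decline, placebo | option of doxycycline | unblinded, offered doxycycline |
| After decline, doxycycline | patient's option to continue or withdraw | withdrawal at the doctor's discretion |
| Who enters the composite | all decliners, either arm | those fulfilling criteria for withdrawal |
| Pneumothorax limb | recurrent pneumothorax | pneumothorax |

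The trigger is common to both arms, and unblinding follows from it, so it is met before the arm is revealed. The rows that differ are who enters the composite, who decides continuation on doxycycline, and the pneumothorax wording.

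**Step 2. Is decline a large part of the composite?** The protocol gives no event rate for the composite, so there is no figure of its own to reproduce. A loss of 300 ml in 24 months needs a slope above 300/2 = 150 ml/year. With normally distributed slopes (an assumption) and the means and SDs in the Sample size section, the share reaching it is 1 − Φ((150 − mean)/SD):

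- UK mean 118, SD 142: 1 − Φ(0.225) = 41.1%
- French cohort 106, SD 143: 1 − Φ(0.308) = 37.9%
- NIH 75, SD 149: 1 − Φ(0.503) = 30.7%
- UK mean 118 with the planned SD 75: 1 − Φ(0.427) = 33.5%
- NIH mean 75 with the planned SD 75: 1 − Φ(1) = 15.9%

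These shares ignore measurement noise. They also ignore the need for two occasions, which lowers them: if the threshold must be reached by month 21 to be confirmed at month 24, the slope must exceed 300/1.75 = 171 ml/year, and 33.5% becomes 1 − Φ((171.4 − 118)/75) = 23.8%. Decline is still not a marginal component.

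**Step 3. Illustration, decline component only.** Assume no drug effect, 20 per arm, a true decline share of 33.5% in both arms (0.335 × 20 = 6.7 patients expected per arm), and an uncorrected two-sided chi-square test at 5%. Let c be the share of doxycycline decliners who are withdrawn. The documents do not give c.

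- Threshold counts in both arms: 33.5% v 33.5%; false significance 5.3%.
- Only withdrawal counts, so placebo has no decline events: with c = 0.25, 0.5 and 0.75, false significance is 8%, 44% and 78%, against doxycycline.
- Mixed counting (every placebo decliner, but only withdrawn doxycycline decliners): with c = 0.25, 0.5 and 0.75, false significance is 52%, 23% and 9%, in favour of doxycycline.

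**Step 4. Illustration, whole composite.** Complications are counted alike in both arms and dilute the effect. Simulation with no drug effect; mean decline 118 ml/year; slope SD 75 or 142; nine readings; assumed visit noise 75 ml; two consecutive falls of 300 ml; assumed 20% two-year complication risk per arm; log-rank test at 5%. The SaO2 limb is not modelled. Ranges cover repeated runs of 2,000 to 3,000 trials.

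| Counting rule | Events, doxycycline v placebo (SD 75; SD 142) | False significance (SD 75; SD 142) |
|---|---|---|
| Threshold, both arms | about 41% each; about 48% each | about 4–6% in both |
| Mixed, c = 0.75 | 35% v 41%; 41% v 48% | 6–8% in both |
| Mixed, c = 0.5 | 30% v 41%; 34% v 48% | 9–11%; 11–15% |
| Mixed, c = 0.25 | 25% v 41%; 27% v 48% | 16–17%; 23–26% |
| Withdrawal only, c = 0.5 | 30% v 20%; 34% v 20% | 10–12%; 14–16% |

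**The case against.** The best defence is that the Combined safety endpoint section counts patients who fulfil the criteria, not patients who are withdrawn. The criteria are the 300 ml and 3% thresholds and the listed complications, and they apply to both arms. The Summary confirms this: it brings all decliners into the composite and applies intention to treat, so a doxycycline patient who continues is still an event. On this reading nothing is biased. This largely stands. A reader might infer that the arms have no common criterion, or that the protocol prescribes unequal counting; the documents support neither.

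A reader might also infer that event dates differ by arm, with the offer dating the placebo event and the withdrawal dating the doxycycline event. Neither section dates the event in that way, and dating rules may sit in an analysis plan that is not at hand.

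It is also fair to say that the mixed rule in Steps 3 and 4 uses two event definitions in one analysis, that c, the noise and the complication risk are assumed, and that near c = 0.75 the mixed rule is close to nominal for the whole composite. The error rates are therefore not estimates for this trial.

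What the defence does not remove is the conflict. The wording ties the event to withdrawal, the FVC entry in section 4 does likewise, and the Summary does not. An analysis plan could choose between the definitions, but the protocol has already stated both.

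**Conclusion.** Wrong as written: the definition of a named secondary endpoint is contradictory. The Summary supports symmetric counting; the Combined safety endpoint section can be read as requiring withdrawal, which after a decline is discretionary on doxycycline and not described on placebo. The threshold reading carries no bias. The withdrawal reading carries a bias whose direction depends on how placebo decliners are treated. With half of doxycycline decliners counted, the whole-composite illustration puts false significance at about 9% to 16% against about 5%; that range depends wholly on the assumed withdrawal share, visit noise and complication risk. The separate differences over pneumothorax and over who decides continuation hold without any assumption. The primary endpoint and the 20 patients per group are not affected.

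**What to change.** In the Combined safety endpoint section, replace the sentence "Patients fulfilling these criteria for withdrawal, together termed the 'composite safety endpoint', will be compared between treatment arms" with wording aligned to the Summary. All randomised patients in either arm who meet the numerical FEV1/SaO2 criterion on two occasions, or who have a listed complication, count as events. Date the event at the visit that confirms the criterion, recorded before unblinding, or at the complication. It counts whatever the expert, doctor or patient then decides about treatment. Edit the Summary to match; it needs its own change, because the replaced sentence does not appear there.

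Reconcile the two sections on recurrent pneumothorax versus pneumothorax, since otherwise that limb stays undefined. Reconcile them also on who decides continuation for doxycycline patients: expert assessment and patient option, or the doctor's discretion. No view is taken here on which is right.

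The cost is protocol wording only. The thresholds must already be measured to trigger the rule, so no extra visits, data or patients are needed.

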## Introduction

### Lymphangioliomyomatosis

Lymphangioliomyomatosis (LAM) is a disease of the lungs and lymphatics, which can occur sporadically or in association with tuberous sclerosis complex (TSC). The disease is rare, occurring in 1-2 / million of the population but in up to 40% of women with TSC LAM almost exclusively affects women, generally developing before the menopause. The disease is characterised by progressive pulmonary cystic change, recurrent pneumothorax, chylous pleural collections and, in most cases, progressive respiratory failure. Abdominal manifestations caused by obstruction and dilation of the axial lymphatics include lymphadenopathy, cystic lymphatic masses (lymphangioliomyomas), chylous ascites and angiomyolipoma (a benign tumour). Survival in LAM is, 70 90% at 10 yrs, although this is highly variable since long-term survivors have been described. Diagnosis is made by a combination of clinical features and computed tomography scanning or, in cases of doubt, lung biopsy. In patients with rapidly progressive disease, hormone treatment (predominantly progesterone) has been used, although no firm evidence supports its use. Otherwise, treatment is aimed at complications including pneumothorax, chylous collections and extra-pulmonary manifestations. The only treatment for severe LAM is currently lung transplantation.

Recently identification of abnormalities in the tuberous sclerosis complex (TSC) genes in sporadic and TSC associated LAM have identified dysregulation of the mTOR pathway in LAM and have lead to clinical trials of mTOR inhibitors such as rapamycin in LAM and TSC. At the time of writing these have not been reported but appear promising.

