### Statistical analysis of endpoints

#### Primary endpoint

The primary endpoint will be the difference in rate of decline of FEV1 (ml/year) measured over 24 months.

All data will be analysed on an intention to treat basis in conjunction with the trial statistician [name]. The mean slope of regression lines for FEV1 and FVC, plus change in DLCO, shuttle walk distance and quality of life in the doxycycline and placebo groups will be compared by parametric or non-parametric analysis as appropriate following analysis of the data for normality. In addition we will perform a *per protocol* analysis of mean rate of change of FEV1/year. Time to composite safety endpoint will be analysed by Kaplan-Meier analysis, complications and adverse events by Chi Square test. Patients withdrawing from the study will continue to have measurements made where possible for intention to treat analysis. Missing values will be handled by multiple imputation.

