#### Secondary endpoints

- The mean of regression lines for FVC measurements for each group (nine measurements per subject) will be compared by unpaired t-test with 0.05 taken as statistical significance. Patients will be analysed on an intention to treat basis with those withdrawing for any reason (including the combined safety criteria) will be analysed up to withdrawal.
- Change DLCO, shuttle walk distance and QoL in the doxycycline and placebo groups will be compared by parametric or non-parametric analysis. Data will be analysed for normality using the Kolmogorov-Smirnov method.

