#### Toxicity and safety

- Time to composite safety endpoint by Kaplan-Meier analysis.
- The number of LAM related complications (pneumothorax, chylous effusions, respiratory infections and angiomylipoma bleeding) in each group will be analysed by Chi Square test.
- The number of doxycycline related side effects (related and unrelated) in each group will be analysed by Chi Square test.

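### The composite safety endpoint is a closed list without death or lung transplantation, so a patient who dies or is transplanted with no earlier listed event is censored

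*Protocol*

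**What the plan says.** Section 3, Combined safety endpoint, names the components. The first is deterioration, meaning a 300 ml FEV1 fall or a fall in resting saturation "of 3% (on two occasions) will be unblinded and offered doxycycline according to the protocol". The second is complications: "patients with either pneumothorax, increase in chylous effusion or bleeding angiomyolipoma will be withdrawn". It then closes the list: "Patients fulfilling these criteria for withdrawal, together termed the 'composite safety endpoint', will be compared between treatment arms". The Summary gives a similar list, but qualifies pneumothorax as recurrent.

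Time to this composite is a secondary endpoint. Section 4, Toxicity and safety, sets the method: "Time to composite safety endpoint by Kaplan-Meier analysis". No rule is given for censoring or competing events.

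Death appears only in the section 5 definition of seriousness and in expedited reporting. There is no mortality endpoint. Transplantation appears as a baseline exclusion and in the Introduction: "The only treatment for severe LAM is currently lung transplantation".

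On data after withdrawal, section 4 says two things. Under Primary endpoint: "Patients withdrawing from the study will continue to have measurements made where possible for intention to treat analysis", followed by "Missing values will be handled by multiple imputation". Under Secondary endpoints, in the FVC item: "those withdrawing for any reason (including the combined safety criteria) will be analysed up to withdrawal".

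**The concern.** Death and transplantation are the end stages of the process that the composite is meant to detect. As defined, neither is an event. Under Kaplan-Meier, a patient who reaches one of them first leaves the risk set as though her later risk matched that of patients still under follow-up. In a progressive lung disease that assumption is not credible. If such cases fall more often in one arm, that arm's event-free curve is too high.

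The component list is fixed in the protocol, so this is not a detail left to the SAP. An SAP may set censoring rules, but adding a component would change the protocol's definition.

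The second, less likely consequence concerns the primary endpoint. FEV1 may be measured after withdrawal, and no sentence excludes readings taken after a lung transplant. Such readings describe donor lung, yet a regression line would take them as improvement.

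**Working it through.** **1. The plan's own figure.** Sample size (section 3): 20 per group, difference 70 ml/year, SD 75 ml/year, 80% power. A two-sided 0.05 level is assumed; the protocol states 0.05 for the FVC test. The standardised difference is 70 / (75 × √(2/20)) = 70 / 23.72 = 2.95. Power is 83.9% by the normal approximation and 82.0% by the exact t-test. With 19 per group the t-test gives 79.9%, so 20 is the smallest adequate size and the figure reproduces. The point does not alter it; 70 ml/year serves below as a yardstick.

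**2. Expected deaths.** Input: 10-year survival S of 70 to 90% (Introduction). Under a constant hazard, two-year risk = 1 − S^0.2 and P(at least one death in 40) = 1 − S^8.

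- S = 0.9: risk 2.1%; 40 × 0.0209 = 0.8 deaths; P = 1 − 0.430 = 57%.
- S = 0.7: risk 6.9%; 40 × 0.0689 = 2.8 deaths; P = 1 − 0.058 = 94%.

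These are all deaths. Those misclassified are the subset with no earlier component event. The likely members are sudden or unrelated deaths, deaths between three-monthly visits before a second confirming reading, and patients with little FEV1 left to lose. The entry criteria set no lower FEV1 limit, and Table E1 gives a doxycycline-arm baseline mean of 1.43 L (SD 0.81). The size of the subset cannot be derived.

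**3. One transplant and the slope.** Assumption, not in the documents: FEV1 steps up by 0.5 to 1.5 L and is still measured at every later visit. The schedule gives nine readings, at 0, 3, …, 24 months. With time in years, the mean is 1 and Σ(t − 1)² = 3.75. The shift in the fitted slope is step × Σ(t − 1 over post-transplant readings) / 3.75; dividing by 20 gives the shift in the arm mean.

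| First post-transplant reading | Sum / 3.75 | Patient's slope shift, ml/year (0.5 to 1.5 L) | Arm-mean shift, ml/year |
|---|---|---|---|
| Month 3 or 24 | 1.00 / 3.75 = 0.267 | 133 to 400 | 7 to 20 |
| Month 6 or 21 | 1.75 / 3.75 = 0.467 | 233 to 700 | 12 to 35 |
| Month 9 or 18 | 2.25 / 3.75 = 0.600 | 300 to 900 | 15 to 45 |
| Month 12 or 15 | 2.50 / 3.75 = 0.667 | 333 to 1000 | 17 to 50 |

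The range is 7 to 50 ml/year, or about 10% to 71% of the 70 ml/year target.

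**4. Effect on the test.** Simulation used normal slopes with SD 75, a true difference of 70 ml/year, and one placebo patient's slope raised by 260 to 833 ml/year. Power of the t-test falls from 82% to 54% at the smaller shift and below 1% at the larger. Power of the Mann-Whitney test falls from about 79% to about 65 to 68%. The protocol chooses between the two kinds of test after checking normality, and such an outlier could lead to the rank test.

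**The case against.** The composite has a stated purpose: it stops treatment being withheld from rapid decliners, and it is defined by withdrawal criteria. It is one of eight secondary endpoints. Deaths are recorded as serious adverse events, the data monitoring committee reviews all adverse events, and adverse events are compared between arms. Many patients approaching death or transplantation would already have met an FEV1, saturation or complication criterion and would count as events. Censoring detail may sit in an SAP that is not at hand.

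Most of this limits the size of the problem without removing it. The protocol presents the composite as a safety comparison between arms, and safety reporting does not correct a survival curve that leaves out its most serious outcomes.

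A reader might infer that all 0.8 to 2.8 expected deaths would be scored as event-free. The documents do not support that, because an earlier component event would already have counted. A reader might also infer that donor-lung readings will certainly enter the primary slope. That is not established either. The protocol gives no transplant rate and no FEV1 step, follow-up after withdrawal is conditional on feasibility, and the FVC item points to stopping at withdrawal. That sentence sits under a secondary endpoint and contradicts the one under Primary endpoint, so FEV1 is left ambiguous.

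**Conclusion.** The omission is plain in the text, and nothing elsewhere in the protocol repairs it. Censoring at death or transplantation follows from the closed list together with Kaplan-Meier, but only for patients with no earlier listed event. Under a constant hazard and survival like that quoted, at least one death among 40 patients has a 57 to 94% chance; the number misclassified is smaller and unknown. In a trial of this size, one or two such cases could matter to the comparison.

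The effect on the primary slope is a conditional risk. It needs an on-study transplant, continued spirometry, and the reading of section 4 that keeps data after withdrawal. Its size, 7 to 50 ml/year per transplanted patient in a 20-patient arm, rests on an assumed step, and a rank test would be much less affected. The point merits an amendment and does not undermine the design.

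**What to change.** 1. In the Summary, Combined safety endpoint and the list of secondary endpoints, define the analysed composite as the existing criteria plus death from any cause and lung transplantation, each dated when it occurs. State that this is an endpoint definition only and changes no withdrawal or treatment rule.
2. In section 4, reconcile the Primary endpoint text with the FVC item, so that one rule says which data after withdrawal are analysed for each endpoint.
3. In the same place, state that lung function and shuttle walk values after lung transplantation are not used for the slope or change endpoints, and that values after death or transplantation are not multiply imputed. Without the second part, the excluded readings would become missing values and be imputed.

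The cost is a few sentences and no new procedures. Deaths are already reported as serious adverse events, and transplants would come to light through hospital admissions, three-monthly visits and monthly calls. The composite becomes slightly broader and takes in some deaths unrelated to LAM. Slopes cut short at transplantation rest on fewer readings and are less precise.
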